4.3 Exclusion criteria

Any patient meeting ANY of the following criteria will be excluded from the study:

1. Locally PSqCC candidate for curative treatment.
2. Prior therapy with an anti-PD-1, anti-PD-L1, or anti-PD-L2 agent.
3. Known hypersensitivity to any of the excipients of INCMGA00012 (retifanlimab).
4. Receipt of anticancer therapy or participation in another interventional clinical study within 28 days before the first administration of study drug; 6 weeks for mitomycin C.
5. Radiotherapy within 14 days of first dose of study treatment with the following caveat:
 - a. 28 days for pelvic radiotherapy.
6. Toxicity of prior therapy that has not recovered to \leq Grade 1 or baseline (with the exception of any grade of alopecia and anemia not requiring transfusion support). Endocrinopathy, if well-managed, is not exclusionary and should be discussed with Sponsor's medical monitor.
7. Major surgery (defined as requiring general anesthesia) or significant traumatic injury within 4 weeks of start of study drug, or patients who have not recovered from the side effects of any major surgery, or patients who may require major surgery during the study.
8. Known active uncontrolled or symptomatic Central Nervous System (CNS) metastases, carcinomatous meningitis, or leptomeningeal disease as indicated by clinical symptoms, cerebral edema, and/or progressive growth. Patients with a history of CNS metastases or cord compression are eligible if they have been definitively treated (e.g., radiotherapy, stereotactic surgery) and are clinically stable off anticonvulsants and steroids for at least 4 weeks before randomization.
9. Cardiovascular: patients that have any of the following within 6 months of randomization: severe/unstable angina, myocardial infarction, symptomatic pericarditis, symptomatic congestive heart failure (New York Heart Association functional classification III-IV), cerebrovascular accident including transient ischemic attack, or symptomatic pulmonary embolism, coronary/peripheral artery bypass graft, ongoing cardiac dysrhythmias of NCI-CTCAE v.5.0 grade \geq 2, including, ventricular arrhythmias –except for benign premature ventricular contractions–, supraventricular and nodal arrhythmias requiring a pacemaker or not controlled with medication, any conduction abnormality requiring a pacemaker or any cardiac arrhythmia not controlled with medication.
10. Metabolic: Uncontrolled hyper/hypothyroidism or diabetes mellitus type 1 (T1DM). Patients with hypothyroidism stable on hormone replacement will not be excluded from the trial. Patients with controlled T1DM on a stable insulin regimen may be eligible for this study.

11. Diagnosis of immunodeficiency or is receiving systemic steroid therapy or immunosuppressive therapy within seven days prior to study treatment initiation.
12. Active autoimmune disease that has required systemic treatment in past 2 years (i.e., with use of disease modifying agents, corticosteroids, or immunosuppressive drugs).
Note: Replacement therapy (e.g., thyroxine, insulin, or physiologic steroid replacement therapy (≤ 10 mg prednisone daily) for adrenal or pituitary insufficiency, etc.) is not considered a form of systemic treatment.
13. Prior allogenic stem cell or solid organ transplantation.
14. Has received a live vaccine within 28 days of the planned start of study drug.
Note: Examples of live vaccines include, but are not limited to, the following: measles, mumps, rubella, chicken pox/zoster, yellow fever, rabies, Bacillus Calmette–Guérin (BCG), and typhoid vaccine. Seasonal influenza vaccines for injection are generally killed virus vaccines and are allowed; however, intranasal influenza vaccines (e.g., FluMist®) are live-attenuated vaccines and are not allowed.
15. Active/history of pneumonitis requiring treatment with steroids or active/history of interstitial lung disease.
16. Active uncontrolled infection at the time of screening.
17. Latent tuberculosis determined by a positive TST followed by confirmation by pulmonologists.
18. Participants who are known to be human immunodeficiency virus (HIV)-positive, unless all of the following criteria are met:
 - a. CD4-positive count $\geq 300/\mu\text{L}$;
 - b. Undetectable viral load;
 - c. Receiving highly active antiretroviral therapy.
19. Active hepatitis A virus (HAV) (positivity for HAV IgM antibody), hepatitis B virus (HBV) (patients with negative hepatitis B surface antigen [HBsAg] test and a positive antibody to HBsAg [anti-HBsAg] test at screening are eligible) or hepatitis C virus (HCV) (patients with a positive antibody to hepatitis C [anti-HCV] are eligible only if polymerase chain reaction [PCR] is negative for virus hepatitis C ribonucleic acid [RNA]).
20. Known additional malignancy that is progressing or requires active treatment, or history of other malignancy within 3 years of study entry with the exception of cured basal cell or squamous cell carcinoma of the skin, superficial bladder cancer, prostate intraepithelial neoplasm, or other noninvasive or indolent malignancy, or cancers from which the participant has been disease-free for >1 year, after treatment with curative intent.
21. Patients have any other concurrent severe and/or uncontrolled medical condition that would, in the Investigator's judgment contraindicate patient participation in the clinical study.

5 TREATMENT

5.1 Formulation, Packaging, and Handling

Study drug packaging will be overseen by the Sponsor's Clinical Trial Supplies department and bear a label with the identification required by local law, the protocol number, drug identification, and dosage. The packaging and labeling of the study drug will be in accordance with Sponsor standards and local regulations. Local packaging in some countries may be different.

The study drug must be stored according to the details on the Product Information. The drug label indicates the storage temperature. Upon arrival of investigational products at the site, site personnel should check them for damage, verify proper identity, quantity, integrity of seals, and temperature conditions, and report any deviations or product complaints upon discovery.

INCMGA00012 (retifanlimab) drug product for IV administration will be supplied in a glass vial for single use. Each vial contains INCMGA00012 (retifanlimab) at a concentration of 25 mg/mL. Upon receipt, INCMGA00012 (retifanlimab) vials are to be refrigerated at 2-8 °C (36-46 °F) in a locked storage area protected from light with limited access. Do not freeze. INCMGA00012 (retifanlimab) vials should not be used beyond the expiration date provided by the manufacturer.

5.2 Dosage and Administration

INCMGA00012 (retifanlimab) should be administered intravenously, at flat dose of 500 mg over one hour (\pm 15 minutes) or 30 minutes (\pm 15 min) using a filter on day 1 of each 28-day cycle (every 4 weeks). Infusion rate may be reduced if an infusion reaction occurs.

INCMGA00012 (retifanlimab) was observed to be compatible with the following materials: polyvinylchloride (PVC) with (2-ethylhexyl) phthalate (DEHP), PVC (without DEHP), polyolefin, polyethylene, polypropylene and polyethersulfone (PES). Study drug administration supplies (i.e., IV bags and tubing) should be made only of these materials.

INCMGA00012 (retifanlimab) will be prepared by adding the drug product directly to a bag containing 0.9% sodium chloride (normal saline) injection United States Pharmacopeia (or local equivalent) and delivered through an IV administration set including a 0.2 micron low protein binding preferably in-line filter made of PES. The final concentration range for INCMGA00012 (retifanlimab) must be within 0.3mg/mL to 12mg/mL in the normal saline IV bag. It is recommended to use 100 mL normal saline IV bags for infusion preparation, however, in case of supply constraints, 250 mL normal saline IV bags may be used if needed.

The total time at room temperature for prepared infusion solution should not exceed 6 hours inclusive of infusion time.

5.3 Treatment Modification

Safety and tolerability of all patients will be closely monitored throughout study treatment and the follow-up period using the NCI–CTCAE v.5.0. Patients will be assessed in order to detect any AEs before administering new study treatment during each treatment visit. Treatment will only be administered if clinical evaluation and local laboratory test results are acceptable.

Patients who have treatments withheld for more than 12 weeks must discontinue study treatment and are considered off study. Patients whose treatment is interrupted or permanently discontinued due to an AE, including abnormal laboratory value, must be followed until resolution or stabilization of the event, whichever comes first, which includes all study assessments appropriate to monitor the event.

Inpatient dose reductions are not permitted for INCMGA00012 (retifanlimab). If a dose interruption is necessary for management of treatment-related TEAEs, INCMGA00012 (retifanlimab) will be reinitiated at the dose at which it was interrupted.

Patients should meet the following re-treatment criteria before proceeding with subsequent cycles:

- Hemoglobin \geq 8 g/dL.
- ANC \geq $1.0 \times 10^9/L$.
- Platelet count \geq $75 \times 10^9/L$.
- ALT/AST/bilirubin level < Grade 2.
- Resolution of all immune-related TEAEs to \leq Grade 1 (with the exception of hyperglycemia [allowed to Grade 2] and endocrinopathy that is controlled on hormonal replacement).
- Resolution of all non-immune-related TEAEs to \leq Grade 1 or baseline (with the exception of Grade 2 alopecia and fatigue). Transient asymptomatic laboratory elevations \leq Grade 3 do not require dose interruption if the participant is asymptomatic and if the elevation is clinically insignificant and has been discussed with the medical monitor.

If retreatment criteria are not met, then re-treatment should be delayed, and the participant should be re-evaluated weekly or more frequently as clinically indicated. INCMGA00012 (retifanlimab) may be interrupted for a maximum of 12 weeks due to toxicity.

5.4 Modification of the Amount of Study Drug Administered Due to Changes in Patient's Weight

INCMGA00012 (retifanlimab) is administered as a fixed dose irrespective of the patient's body weight. AEs (both non-serious and serious) associated with INCMGA00012 (retifanlimab)

exposure may represent an immunologic etiology. These AEs may occur shortly after study treatment initiation or several months after the last dose of treatment. INCMGA00012 (retifanlimab) must be withheld for certain drug-related toxicities and severe or life-threatening AEs as per **Table 1** below. Dose reduction of INCMGA00012 (retifanlimab) is not permitted.

INCMGA00012 (retifanlimab) should be permanently discontinued:

- For grade 4 toxicity except for endocrinopathies that are controlled with replacement hormones.
- If steroid dosing cannot be reduced to ≤ 10 mg prednisone or equivalent per day within 12 weeks.
- If a treatment-related toxicity does not resolve to grade 0-1 within 12 weeks after last dose of INCMGA00012 (retifanlimab).
- If any event occurs a second time at grade ≥ 3 severity (also for recurrent grade 2 pneumonitis).

Table 1. Toxicity Management Guidelines for Immune-related AEs Associated with INCMGA00012 (retifanlimab).

Immune-Related Adverse Event	Toxicity Grade or Conditions (CTCAE v5.0)	Action Taken With INCMGA00012 (retifanlimab)	AE Management With Corticosteroid and/or Other Supportive Care Therapies
Pneumonitis	Grade 1	No action.	None.
	Grade 2	Withhold until \leq Grade 1.	
 Administer systemic corticosteroids per local practice followed by taper. Evaluate participants with suspected pneumonitis with radiographic imaging and initiate corticosteroid treatment. Add prophylactic antibiotics for opportunistic infections.
	Grades 3 or 4, or recurrent Grade 2	Permanently discontinue.	
Diarrhea/colitis	Grade 1	No action.	None.
	Grades 2 or 3	Withhold until \leq Grade 1.	
 Consider prompt initiation of standard anti-diarrheal agents. Administer systemic corticosteroids per local practice followed by taper. Consider prophylactic antibiotics per local practice. Consider gastrointestinal consultation and performing endoscopy to rule out colitis.
	Grade 4 or recurrent Grade 3	Permanently discontinue.	
AST/ALT elevation and/or increased bilirubin/Hepatitis	Grade 1	No action.	None.
	Grade 2	Withhold until \leq Grade 1.	
 Administer systemic corticosteroids per local practice followed by taper. Consider monitoring liver enzymes weekly (or more frequently) until liver enzyme value returns to baseline or is stable.
	Grade 3 or 4, or in participants with liver metastasis with baseline Grade 2 elevation of AST or ALT, hepatitis with AST or ALT increases \geq 50% and lasts \geq 1 week	Permanently discontinue.	
Endocrinopathies Type 1 diabetes mellitus	Grades 1 and 2	No action.	None.
	Grades 3 and 4 hyperthyroidism	No action.	For hypothyroidism, initiate thyroid replacement hormones (eg, levothyroxine or liothyronine) per standard of care.

Immune-Related Adverse Event	Toxicity Grade or Conditions (CTCAE v5.0)	Action Taken With INCMGA00012 (retifanlimab)	AE Management With Corticosteroid and/or Other Supportive Care Therapies
Hyperglycemia Hyperthyroidism Hypothyroidism Hypophysitis Adrenal insufficiency	Grades 3 or 4	Withhold until \leq Grade 1. May restart INCMGA00012 (retifanlimab) if endocrinopathy has improved to \leq Grade 2 and is controlled with hormone replacement, if indicated, and steroid taper is complete.	
 For Type 1 diabetes mellitus, initiate insulin replacement therapy. For hyperglycemia, administer antihyperglycemic. For hyperthyroidism, treat with nonselective beta-blockers (eg, propranolol) or thionamides as appropriate. For hypophysitis or adrenal insufficiency, administer corticosteroids and initiate hormonal replacements as clinically indicated.
Nephritis and renal dysfunction	Grade 1	No action.	None.
	Grade 2	Withhold until \leq Grade 1.	Administer corticosteroids per local practice followed by taper.
	Grade 3 or 4	Permanently discontinue.	
Rash	Grade 1	No action.	None.
	Grade 2	No action.	Manage with topical steroids with or without drug interruption.
	Grade 3 ⁱ⁾ or persistent Grade 2 (\geq 2 weeks) or suspected Stevens-Johnson syndrome or toxic epidermal necrolysis	Withhold until \leq Grade 1.	Administer corticosteroids per local practice followed by taper.
	Grade 4 or confirmed Stevens-Johnson syndrome or toxic epidermal necrolysis	Permanently discontinue.	
Myocarditis	Grade 2	Withhold until \leq Grade 1.	
 Treatment with systemic corticosteroids should be initiated (initial dose of 1-2 mg/kg per day of prednisone or equivalent). Taper as appropriate. Management of cardiac symptoms according to standard of care and with guidance from cardiology. Consider cardiac MRI and myocardial biopsy for diagnosis.
	Grades 3 or 4	Permanently discontinue.	
All other irAEs	Grade 3 or intolerable/persistent Grade 2	Withhold until \leq Grade 1.	Based on severity of AE, administer corticosteroids.
	Recurrent Grade 3	Consider discontinuation.	
	Grade 4	Permanently discontinue.	

Table 2. Guidelines for Management of Suspected Infusion Reactions.

Grade	Description ⁱ⁾	Treatment	Subsequent Infusions
1	Mild reaction; infusion interruption not indicated; intervention not indicated.	
 • Monitor vital signs closely until medically stable. 	
 • Premedication with acetaminophen/paracetamol and a histamine blocker should be considered for participants who have had previous systemic reactions to protein product infusions or when recommended by institutional policy.
2	Requires infusion interruption but responds promptly to symptomatic treatment (e.g., antihistamines, non-steroidal anti-inflammatory drugs [NSAIDS], narcotics, IV fluids); prophylactic medications indicated for ≤ 24 hours.	
 • First occurrence: Stop infusion and initiate appropriate medical measures (e.g., IV fluids, antihistamines NSAIDS, acetaminophen/paracetamol, narcotics, per institutional preferences). • Monitor vital signs until medically stable. • If symptoms resolve within 1 hour, infusion may be resumed at 50% of the original infusion rate. • Subsequent occurrences (after recommended prophylaxis): Permanently discontinue study treatment. 	
 • Premedicate at least 30 minutes before infusion with antihistamines (e.g., diphenhydramine 50 mg orally) and acetaminophen/paracetamol (500-1000 mg orally). • Additional supportive measures may be acceptable (per institutional preference) but should be discussed with medical monitor. • Next infusion should start at 50% of the original infusion rate. If no reaction, rate of infusion can be increased by 25% every 15 minutes until a rate of 100% has been reached. Subsequent infusions can begin at 100%.
3 or 4	
Grade 3: Prolonged (i.e., not rapidly responsive to symptomatic medication and/or brief interruption of infusion); recurrence of symptoms following initial improvement; hospitalization indicated for other clinical sequelae (e.g., renal impairment, pulmonary infiltrates).
 
Grade 4: Life-threatening; pressor or ventilatory support indicated.
	
 • Stop infusion and initiate appropriate medical therapy (e.g., IV fluids, antihistamines NSAIDS, acetaminophen/paracetamol, narcotics, oxygen, pressors, epinephrine, corticosteroids, per institutional preferences). • Monitor vital signs frequently until medically stable. Hospitalization may be indicated. 	
 • Permanently discontinue study treatment.

ⁱ⁾ Per NCI–CTCAE v5.0, appropriate resuscitation equipment should be available at the bedside and a physician readily available during the period of study treatment administration.

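### Table 1 prescribes no action for grade 3 and 4 hyperthyroidism, against its own withhold row, the Section 5.3 re-treatment criteria and, for grade 4 or recurrent events, the Section 5.4 stopping list

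*Protocol*

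**What the plan says.** Section 5.4 says the drug must be withheld for certain toxicities as set out in Table 1. The endocrine block of that table lists hyperthyroidism and hypothyroidism among its conditions. One row is labelled "Grades 3 and 4 hyperthyroidism" and its action cell reads no action. The management text on that row, as extracted, is "For hypothyroidism, initiate thyroid replacement hormones (eg, levothyroxine or liothyronine) per standard of care".

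The next row, for grades 3 or 4, says to withhold until grade 1 or less. It then adds "May restart INCMGA00012 (retifanlimab) if endocrinopathy has improved to" grade 2 or less "and is controlled with hormone replacement, if indicated, and steroid taper is complete". Its management column includes "For hyperthyroidism, treat with nonselective beta-blockers (eg, propranolol) or thionamides as appropriate".

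Section 5.3 lists what patients should meet before each further cycle. One item is "Resolution of all immune-related TEAEs to" grade 1 or less. The exceptions are hyperglycemia to grade 2 and "endocrinopathy that is controlled on hormonal replacement". If the criteria are not met, the dose is delayed.

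The Section 5.4 list calls for permanent discontinuation at grade 4, except for endocrinopathies controlled with replacement hormones. It also does so when any event occurs a second time at grade 3 or higher, or when a treatment-related toxicity has not resolved to grade 0-1 within 12 weeks of the last dose.

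For recurrent grade 3 events among all other immune-related events, Table 1 only asks the site to consider discontinuation.

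**The concern.** A site with a severe thyroid result finds two rows in one table that give opposite instructions for the same event, and the protocol does not say which text takes precedence. The mandatory wording in Section 5.4 points to Table 1, whereas the Section 5.3 criteria and the stopping list are phrased as things that should happen. The specific hyperthyroidism row could therefore be taken to override the general rules. Thyroid function is scheduled at every cycle (Appendix 1), so sites will consult this part of the table.

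What is at stake is patient safety and consistent dosing across sites. If the label is a slip, the table also lacks the row it was meant to have, and a patient whose severe hypothyroidism is controlled could be held off drug under the withhold row. The sample size, the ORR test and the rest of the analysis do not depend on this.

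**Working it through.** The plan gives no figure on this point, so the check is a comparison of instructions, followed by a rough estimate of how often they would matter.

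**Instructions side by side**

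| Situation | Hyperthyroidism row | Withhold row | Section 5.3 | Section 5.4 list |
|---|---|---|---|---|
| First grade 3 hyperthyroidism | Continue | Withhold | Delay until grade 1 or less | Not triggered if it resolves within 12 weeks |
| Second event at grade 3 or higher | Continue | Withhold | Delay | Stop permanently |
| Grade 4 hyperthyroidism | Continue | Withhold | Delay | Stop permanently |

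The replacement exceptions in Sections 5.3 and 5.4 do not rescue the first column. Hyperthyroidism is an excess of hormone, and Table 1 treats it with beta-blockers or thionamides.

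**Is the label a slip?** Three observations suggest that hypothyroidism was meant:
- The management text on the row concerns hypothyroidism.
- Hyperthyroidism has its own treatment bullet in the withhold row.
- No action for hypothyroidism would agree with the Section 5.3 exception and the Section 5.4 grade 4 exception once the patient is controlled on replacement.

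The first observation is the weakest. The block is split at a page break, so the alignment of cells is uncertain. A relabelled row would also overlap the withhold row, which lists hypothyroidism too.

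**How often it could arise.** Inputs: protocol Table 4, retifanlimab monotherapy, N = 578, any grade; planned enrolment 18. Expected cases = 18 × k/578.
- Hyperthyroidism: 27/578 = 4.67%; 18 × 27/578 = 0.84.
- Hypothyroidism: 47/578 = 8.13%; 18 × 47/578 = 1.46.

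The documents give no grade 3-4 share for either event. With an assumed share s, the chance of at least one grade 3-4 case is 1 − (1 − s × k/578)^18:

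| Assumed s | Hyperthyroidism | Hypothyroidism |
|---|---|---|
| 2% | 1.7% | 2.9% |
| 10% | 8.1% | 13.7% |
| 20% | 15.5% | 25.6% |

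The hypothyroidism column largely describes situations that the replacement exceptions already cover.

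**Recurrent grade 3 among other immune-related events.** The nonendocrine events in Table 4 without their own Table 1 row are myositis 3, polyarthritis 3, pancreatitis 2, uveitis 2 and radiculopathy 1. They sum to 11, and 11/578 = 1.9%. Counting each event as a separate patient, 18 × 11/578 = 0.34 expected at any grade. Recurrent grade 3 events would be a small part of that.

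**The case against.** The strongest reply is that nobody following the protocol as a whole would dose such a patient. The adjacent row names hyperthyroidism and withholds it. Section 5.3 is applied before every later dose, four weeks apart, and also requires acceptable clinical and laboratory results. No thyroid event appears in the grade 3 or higher lists that Section 1.6.3 gives for studies 101, 104, 202 and 203, although three of those lists have reporting thresholds. This reply stands as to size. It does not remove the contradiction, because the no-action row is explicit and nothing in the protocol overrides it.

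A reader might infer that the protocol permits treatment through life-threatening hyperthyroidism. The documents do not support that: one row, taken alone, says so, while the same table and Sections 5.3 and 5.4 say otherwise. A reader might also infer that every grade 3 case contradicts the stopping list. A first grade 3 event that resolves in time does not trigger it.

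Nor are the restart clause and the advice to consider discontinuation outright contradictions. Both are permissive. A site that restarts only at grade 1 or less, and stops at recurrent grade 3, complies with every text.

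**Conclusion.** The no-action instruction for grade 3 and 4 hyperthyroidism is wrong as printed. It contradicts the withhold row and Section 5.3 at both grades, and the Section 5.4 list for grade 4 or a second event at grade 3 or higher. That the intended word was hypothyroidism is likely but not established.

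The practical risk is small. Fewer than one hyperthyroidism case of any grade is expected in 18 patients, on the assumption that the pooled monotherapy rate carries over to this population. The grade 3-4 probabilities rest on assumed shares and only indicate scale. The point still merits correction, because it is a dosing rule for severe toxicity and the remedy is cheap. The wording for recurrent grade 3 other events is a secondary matter of alignment.

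**What to change.** With the medical lead confirming the intent:

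1. Relabel the row for grade 3 and 4 hypothyroidism, with no action once controlled on hormone replacement, and exempt such cases from the withhold row. If the printed label was intended, replace no action with withholding.
2. State that grade 3 hyperthyroidism is withheld until grade 1 or less, and that grade 4 hyperthyroidism is permanently discontinued under Section 5.4. This also settles the restart clause for hyperthyroidism.
3. As a secondary item, align the recurrent grade 3 cell for other immune-related events with the Section 5.4 recurrence bullet, or write the exception into that bullet.

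I would not add a general sentence that the stricter text prevails, because it would change dosing elsewhere. Grade 2 rash is now handled by "Manage with topical steroids with or without drug interruption" and would have to be delayed under Section 5.3. The same would apply to grade 2 endocrinopathies not covered by a Section 5.3 exception, and to tolerable, non-persistent grade 2 other events. A second grade 3 hypothyroidism, even if controlled, would mean stopping, because the recurrence bullet has no endocrine exception.

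The cost is a protocol amendment of about three Table 1 cells, possibly a line in Section 5.4, and a notification to sites. Sample size, endpoints and the ORR analysis do not change.
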